6.4.1 Arm A (Intervention – Standard Care and Serial MRIs)

Immobilisation discontinued on the basis of MRI defined disease resolution at 3, 6, 9 or 12 months

In the intervention arm participants will receive additional MRIs at 3, 6, 9 and 12 months. Patients randomised to serial MRI will not undergo further MRI once remission has been diagnosed i.e. if remission is diagnosed at 6 months the MRI at 9 and 12 months will not occur.

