6.4.2 Arm B (Control – Standard Care and one additional MRI)

Immobilisation discontinued on the basis of clinical remission determined by skin temperature measurement and MRI. In the standard care arm participants will receive one additional MRI when the temperature measurements, X-ray and/or signs and symptoms indicate to the clinical team that the foot is in remission.

A temperature difference of $\leq 2^{\circ}\text{C}$ which is maintained or improves on two separate consecutive occasions for a period of ≥ 4 weeks will be the indicator to arrange the second MRI, to confirm the diagnosis of remission.

If participants in either arm of the trial have not reached remission at the end of the 12 month active phase of the study they will exit the study. Ongoing standard care will be provided by their clinical team.

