6.5.2 Exploratory Clinical Outcomes

- Days with immobilisation, measured at the end study
- Progression of foot deformity as documented by measuring radiological foot alignment angles. All x-rays will be taken in a weight bearing position with standard views as per WPD. Comparison from baseline, diagnosis of remission, and six months after remission. The angles that will be assessed are:
 - Calcaneal Inclination – the angle formed by the horizontal and a line from the base of the heel and inferior cortex of the calcaneus
 - Talar Declination – the angle between the line originating from the centre of the talus bisecting the talar neck and head and the weight bearing plantar surface from the calcaneus to the 5th metatarsal
 - Talo-first metatarsal angle – the angle between the line originating from the centre of the talus bisecting the talar neck and head, and the line through the longitudinal axis of the first metatarsal.

- Hindfoot-forefoot angle - the angle between the talocalcaneal bisector and the second metatarsal shaft
- Cuboid height (mm) - the distance from the plantar aspect of the cuboid to a horizontal line drawn from the plantar calcaneal tuberosity to the fifth metatarsal head.

Patients who have undergone previous minor amputation and/or previous orthopaedic surgical fixation of the foot altering/removing the anatomical landmarks of the foot will be excluded from this analysis due to the absence of bony landmarks.

At each study visits the following will be measured and recorded on the eCRF:

- Number of new ulcerations on the index foot
- Number of new ulcerations on the contralateral foot
- Number of new infections on the index foot
- Number of new infections on the contralateral foot
- Number and severity of falls (Hopkins Fall Grading System)¹
- Number of minor and major amputations on the index foot at the end of the follow up phase of the study
- Number of minor and major amputations on the contralateral foot at the end of the follow up phase of the study
- The number of participants in each arm requiring further intervention for CN (e.g. further immobilisation) within 6 months of remission

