6.6 Participant Timeline

	Active Phase (fortnightly visits throughout active phase of trial)										Remission	Follow Up after remission diagnosed			
Visit Number	1		6		11		18		25			FUV1	FUV2	FUV3	FUV4
month			3m		6m		9m		12m			1month	2months	3months	6months
Week **	0	2 weekly	W12	2 weekly	26	2 weekly	40	2 weekly	52						
Check In/exclusion criteria *	*														
Hand out FIS *	*														
Consent *	*														
Randomisation *	*														
Medical History *	*														
Foot Surgical history *	*														
Medication *	*	*	*	*	*	*	*	*	*	*	*	*	*	*	*
Record any amputation/s *	*	*	*	*	*	*	*	*	*	*	*	*	*	*	*
Record any infection/s *	*	*	*	*	*	*	*	*	*	*	*	*	*	*	*
Record any ulceration/s *	*	*	*	*	*	*	*	*	*	*	*	*	*	*	*
Record any falls *	*	*	*	*	*	*	*	*	*	*	*	*	*	*	*
Hand out patient diary *	*	*	*	*	*	*	*	*	*	*	*				
Collect & upload diary *		*	*	*	*	*	*	*	*	*	*				
Foot temperatures *	*	*	*	*	*	*	*	*	*	*	*	*	*	*	*
MRI (usual care) **	*									*					
MRI (Intervention arm) **	*		*		*		*		*						
Classification *	*														
Neuropathy Assess *	*														
Vascular Assess *	*														
BMI *	*		*		*		*		*		*				*
HbA1c (use existing if <3months) *	*														
Pain VAS *	*		*		*		*		*		*				*
HADS *	*		*		*		*		*		*				*
SF-12 *	*		*		*		*		*		*				*
EQ5D *	*		*		*		*		*		*				*
Study specific X-ray															*
		← Duration of active phase of treatment will be variable →													
Patient Interviews		← →													

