6.7.2 The “active phase” – up to 12 months

These visits will take place in the participant’s usual place of care (secondary care). Participants will attend for fortnightly visits. Standard care and study specific procedures will be carried out and recorded on the eCRF.

Study Specific Procedures

- The temperature assessment as per the WPD
- The participant diary will be collected and another issued for participants to complete over the next 2 weeks, until their next study visit.

In both arms remission will be defined as an absence of sub-chondral bone marrow oedema on MRI, as reported by a specialist musculoskeletal radiologist and/or the absence of clinical signs and symptoms of CN. The clinical team will interpret the results of the MRI report to determine remission. As per standard care at this point patients will have a foot and ankle X-ray.

Participants who develop bilateral CN during the study can continue in the trial. The trigger to arrange the MRI in the standard care arm will be based on the absence of signs and symptoms of active CN as assessed by the clinical team.

Patients randomised to A (Intervention – Serial MRI)

Patients randomised to the intervention group will have an MRI of their foot and ankle three monthly (at 3, 6, 9 and 12 months) until the CN has settled. Where possible the scan should be scheduled to coincide with study visits to minimise the number of additional hospital visits.

For participants in the intervention arm if the MRI report indicates to the clinical team that the CN is not in remission participants will continue in the active phase of the study, up to a maximum of 12 months.

Patients randomised to B (Standard Care)

Patients randomised to the standard care will undergo an MRI once the temperature difference between their feet is $\leq 2^{\circ}\text{C}$ on two separate occasions at least four weeks apart.

For participants in the standard care arm if the MRI report indicates to the clinical team that the CN is not in remission participants off-loading will be recommenced. Participants will continue in the follow up phase as per the trial protocol.

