6.7.4 Follow up phase

In both arms once remission is confirmed by the MRI patients will then enter a rehabilitation/weaning phase. They will be transferred into a less restrictive off-loading device and then finally into footwear as per standard care. Participants will continue to attend for monthly trial visits for 3 months to monitor for any sign of relapse. The final visits will be at 6 months post remission. Standard care will continue to be provided.

At each visit study specific procedures will be carried out:

- The temperature will be assessed as per the WPD
- The participant diary will be collected and another issued for participants to complete until their next study visit. (This is only for the first three follow-up visits)

In addition to standard care and study specific procedures the participant will be asked to complete the following questionnaires and additional tests/investigations:

Follow Up - Month 1: VAS, SF-12, HADS and EQ-5D-5L will be completed.

Follow UP Month 6: VAS, SF-12, HADS and EQ-5D-5L completed. BMI will be recorded and an X-ray of the foot and/or ankle will be taken.

Relapse will be defined as a temperature difference of $>2^{\circ}\text{C}$ compared to the contralateral foot maintained for two or more occasions or further changes on imaging¹⁵. As per standard care the final decision as to whether the participant has relapsed will be at the discretion of the clinic team. If this occurs, then the participant will then recommence off-loading with a non-removable device. They will continue to be followed up as per the study protocol.

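### Length of observation depends on remission, so event counts to the end of study have no common window; and section 6.7.2 conflicts with 6.7.3 and 6.7.4 on who enters follow-up

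*Protocol*

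**What the plan says.** Two rules in the Protocol fix when a participant stops being observed.

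- Section 6.4.2, for either arm: those who "have not reached remission at the end of the 12 month active phase of the study they will exit the study".
- Section 6.7.4, for remitters: "The final visits will be at 6 months post remission".

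Remission dates vary by participant. For Arm A, section 6.4.1 has "Immobilisation discontinued on the basis of MRI defined disease resolution at 3, 6, 9 or 12 months". For Arm B, section 6.7.2 triggers the MRI when the temperature criterion is met "on two separate occasions at least four weeks apart". The timeline in section 6.6 notes "Duration of active phase of treatment will be variable".

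The events are counted to an end point that moves with these dates. Section 6.5.2 lists "Number of minor and major amputations on the index foot at the end of the follow up phase of the study", with the same item for the other foot. Section 6.11.4.2 counts ulcers, infections, falls and amputations from randomisation to the end of the study. Several of these events are also the safety outcomes in section 6.12.3.1.

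On entry to follow-up, section 6.7.4 says "In both arms once remission is confirmed by the MRI patients will then enter a rehabilitation/weaning phase", and section 6.7.3 also opens the phase on remission. Section 6.7.2 says of standard-care participants whose MRI does not show remission: "Participants will continue in the follow up phase as per the trial protocol". Arm A participants with the same result stay in the active phase.

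**The concern.** The period over which a participant's events are counted depends on whether and when that participant remits. Remission comes after randomisation and is what serial MRI is intended to bring forward. A crude count to the end of study therefore compares arms over windows that treatment may have altered, and it is not a clean intention-to-treat contrast. Participants who exit at month 12 never enter the follow-up phase at whose end section 6.5.2 counts amputations, and they contribute no post-remission observation.

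The second problem is operational. For a standard-care participant whose MRI shows no remission, a site cannot tell whether the active-phase or the follow-up schedule applies. That choice determines visits, questionnaires and the last date on which events are recorded.

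A smaller reporting gap follows. Section 6.5.1 limits withdrawal to loss of consent or death, and section 6.7.8 treats loss to follow-up as failed contact. A month-12 exit is neither, so a possibly large group would appear in neither retention figure.

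**Working it through.** **Inputs from the Protocol.** Exit at month 12 without remission (6.4.2). Last visit at remission plus 6 months (6.7.4). Scans at 3, 6, 9 and 12 months in Arm A (6.4.1). A four-week minimum for the Arm B trigger (6.7.2). Thirty participants per arm (6.8). UK median time to remission of 9 to 12 months (5.1).

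**The plan's own figure.** Section 5.3 gives 12 + 6 = 18 months per participant. This is reproduced, but only as the maximum, for remission at month 12.

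**Observation per participant.** If remission is at month R ≤ 12, observation is R + 6 months; otherwise it is 12.

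| Remission month | Observation (months) |
|---|---|
| 3 | 9 |
| 6 | 12 |
| 9 | 15 |
| 12 | 18 |
| none by 12 | 12 |

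In Arm B the earliest case is about 0.9 + 6 ≈ 7 months. The 9-to-18 range for Arm A holds if remission is dated at the scans. Section 6.7.2 defines remission by MRI and/or absence of clinical signs, which allows other dates.

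**Assumptions for size.** Remission times follow a Weibull distribution with shape k = 1, 1.5 or 2. Control medians are 9, 10.5 or 12 months. The MRI-arm median is 6 or 7 months (assumed effect) or equal to control (no effect). That makes 27 scenarios, 18 of them with an effect. Deaths, withdrawals and alternative diagnoses are ignored.

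**Month-12 exits.** S(12) = 0.5^((12/median)^k), and exits = 30 × (S_control + S_MRI).
- Effect, lowest (k = 2, medians 9 and 6): 30 × (0.292 + 0.062) = 10.6.
- Effect, highest (k = 1, medians 12 and 7): 30 × (0.500 + 0.305) = 24.1.
- No effect: 30 × (0.292 + 0.292) = 17.5, to 30 × (0.500 + 0.500) = 30.

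The range is about 11 to 30 of 60. At a median of 12 months, the 50% needs no distributional assumption.

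**Mean total observation, MRI arm over control** (by simulation). With Arm A remission dated at the scans the ratio is 1.04 to 1.08; with continuous dating it is 0.93 to 1.00. The arms differ by at most about 1 month on average.

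**Planned post-remission observation.** This is 6 × (1 − S(12)) months per arm. With an effect it is 3.0 to 4.25 in control and 4.2 to 5.6 in the MRI arm, a within-scenario gap of about 0.6 to 2.6 months. With no effect it is equal.

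**The same gap if everyone were observed for 18 months.** It is 1.4 to 5.4 months with continuous dating and 0.1 to 3.9 with scan dates, and larger than planned in 13 of the 18 effect scenarios with scan dates.

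**Entry to follow-up.** Sections 6.7.3 and 6.7.4 require remission, the latter confirmed by MRI. Section 6.7.2 puts standard-care participants without MRI remission in follow-up. These conflict directly. The conflict with section 6.4.2 arises only for those still not in remission at month 12, whom one section has in follow-up and the other has leave.

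**The case against.** The strongest defence is that follow-up to 6 months after remission is deliberate. Section 6.5.2 includes further intervention within 6 months of remission, and that outcome needs remission-anchored visits. Nobody was promised 18 months. Events are recorded at each visit, so rates per person-time can be computed from planned data, and section 6.11.4.1 already allows Poisson models. Time to the end of immobilisation can be censored at month 12 in the Cox model. The study is unpowered and its clinical outcomes are exploratory.

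Most of this stands. The remission-anchored visits should stay, and a missing exposure term is not the finding, since an analysis plan may supply it. What remains is that the Protocol itself defines counts to an end date that depends on remission. An exposure term corrects for length; it neither supplies events after visits end nor balances time before and after remission.

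On entry to follow-up, one can read section 6.7.2 as dating follow-up from clinical remission, with off-loading then restarted much as after a relapse. That softens the conflict with section 6.4.2. It does not remove the conflict with MRI confirmation in section 6.7.4 or the different handling of the two arms.

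Section 6.4 already states that participants who do not reach the 6-month post-remission point will not have that X-ray, so its absence is disclosed.

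A reader might go further and infer that longer post-remission observation in the MRI arm tilts ulcer counts against it, citing the 6% acute and 31% chronic ulceration figures in section 5.1. The Protocol does not support that. It gives no follow-up length for those figures and links the chronic ulcers to footwear design, late delivery and compliance, so they give no rate for the first 6 months after remission.

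**Conclusion.** The point holds, with moderate importance. By the Protocol's own rules observation runs from about 7 to 18 months in remitters and is 12 months in exits, so the event counts in sections 6.5.2 and 6.11.4.2 have no common window. The defect lies in the individual spread, in the absence of post-remission observation for an assumed 11 to 30 of 60 participants, and in crude counts that do not give a clean intention-to-treat comparison.

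It does not lie in a large difference in total exposure between arms, which is at most about 1 month on average under the assumptions. No direction of bias is established. These sizes rest on assumed remission distributions and MRI-arm medians; the dependence of the window on remission, and the conflict of section 6.7.2 with 6.7.3 and 6.7.4, rest on the text alone. Sections 5.2 and 6.11.4.1 make the clinical comparisons exploratory, which limits the consequences.

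**What to change.** 1. Reconcile sections 6.4.2, 6.7.2, 6.7.3 and 6.7.4 on which observation schedule applies to standard-care participants whose MRI shows no remission. This concerns visits and data collection; no clinical rule is proposed. The cost is wording only.

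2. In sections 6.5.2 and 6.11.4.2, replace crude counts to the end of study with events per person-time, shown before and after remission, and state that the window depends on remission. This uses planned data.

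3. Report month-12 protocol exits by arm, separately from withdrawal and loss to follow-up. Note in section 6.5.2 that these participants have no planned deformity comparison after baseline. The cost is a line in the participant flow.

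4. Optionally, check clinic records to 18 months from randomisation for ulcers, infections, falls and amputations, and report the source of each event. This gives a common-window intention-to-treat count and fits within the trial end in section 6.7.9. It needs an amendment with consent wording and a check for most participants (about 54 to 57 of 60 have visits ending before month 18 under the assumptions above), and section 7.9 expects no further external funding. Records may miss events that visits would catch. It does not equalise post-remission time between arms, so item 2 is still needed.

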6.4.3 Qualitative Study

There are no existing qualitative studies exploring participant's experiences and perspectives on the management of CN.

The purpose of this qualitative study is to understand the personal experiences of being treated for CN and the participant's experience of being involved in this trial.

The objectives are twofold;

1. To describe the impact of being treated for CN on participants

The domains of the questions will include:

- The personal experience of being treated for CN (e.g. impact on day to day functional activities, employment, leisure pursuits, ability to conduct physical activity, sense of self and self-worth)
- The impact this has had on family members and relationships

- The impact on social participation.
2. Identify ways of refining the trial protocol to improve participant's experience of being involved in any future research; increasing recruitment and retention.

The domains of the questions will include:

- The perceived accuracy of the different approaches to disease monitoring used in the study
- The perceived burden (or otherwise) of the different approaches to disease monitoring
- The participants willingness to be randomised
- The participant's ideas for improvements that could be made to the study to enhance recruitment and retention

In collaboration with PPI representatives these domains will be developed into an indicative topic guide.

As part of the consent form for the main trial participants will be asked whether they would be happy to be approached during the course of the trial to participate in an interview.

The interview will take the format of an interpretative descriptive approach.

A purposive sample of 10-14 participants across both sites will be selected. Diversity across the sample will be ensured by taking into account randomisation arm, treatment times, employment status, gender and age.

Participants approached for the Qualitative study will receive a further information sheet explaining the purpose of the interview and would be consented prior to the interview taking place.

Interviews will last approximately 30-40 minutes in a place of the participants choosing. The interviews will be audiotaped (with participants' permission) and transcribed in full.

6.4.4 Compliance and Adherence

6.4.5 Concomitant Care

All patients will receive treatment as standard for their CN regardless of randomisation into this trial. This will be recorded on the eCRf and form part of the data for this study;

6.4.6 Protocol Treatment Discontinuation

In consenting to the trial, participants are consenting to trial treatments, trial follow-up and data collection. However, an individual participant may stop treatment early or be stopped early for any of the following reasons:

- Adverse event which in the opinion of the treating clinician makes them unsuitable for continued participation in the study
- Inter-current illness that prevents further treatment

- Any change in the participant's condition that in the clinician's opinion justifies the discontinuation of treatment
- Participants who become pregnant during the trial can continue in the trial. They will be excluded from the final X-ray at 6 months post remission.
- Withdrawal of consent for treatment by the participant
- Participant who moves away from the area or decides to transfer to a different hospital for the management of their CN.

As participation in the trial is entirely voluntary, the participant may choose to discontinue trial treatment at any time without penalty or loss of benefits to which they would otherwise be entitled. Although not obliged to give a reason for discontinuing their trial treatment, a reasonable effort should be made to establish this reason, whilst remaining fully respectful of the participant's rights.

Participants who discontinue protocol treatment, for any of the above reasons, should remain in the trial for the purpose of follow up and data analysis.

6.5 Outcomes

6.5.1 Feasibility Outcomes

- The proportion of patients who meet eligibility criteria
- The number of eligible patients recruited
- The number of participants in which an alternative diagnosis of the foot disease is made during the intervention phase of the trial
- The proportion of patients that withdraw or are lost to follow up. The term 'withdrawal' encompasses two potential scenarios; withdrawal due to loss of consent or withdrawal due to death
- Statistical estimation for key outcome measures to inform a sample size calculation for a definitive trial
- Feasibility of quality of life and resource data collection

6.5.2 Exploratory Clinical Outcomes

- Days with immobilisation, measured at the end study
- Progression of foot deformity as documented by measuring radiological foot alignment angles. All x-rays will be taken in a weight bearing position with standard views as per WPD. Comparison from baseline, diagnosis of remission, and six months after remission. The angles that will be assessed are:
 - Calcaneal Inclination – the angle formed by the horizontal and a line from the base of the heel and inferior cortex of the calcaneus
 - Talar Declination – the angle between the line originating from the centre of the talus bisecting the talar neck and head and the weight bearing plantar surface from the calcaneus to the 5th metatarsal
 - Talo-first metatarsal angle – the angle between the line originating from the centre of the talus bisecting the talar neck and head, and the line through the longitudinal axis of the first metatarsal.

- Hindfoot-forefoot angle - the angle between the talocalcaneal bisector and the second metatarsal shaft
- Cuboid height (mm) - the distance from the plantar aspect of the cuboid to a horizontal line drawn from the plantar calcaneal tuberosity to the fifth metatarsal head.

Patients who have undergone previous minor amputation and/or previous orthopaedic surgical fixation of the foot altering/removing the anatomical landmarks of the foot will be excluded from this analysis due to the absence of bony landmarks.

At each study visits the following will be measured and recorded on the eCRF:

- Number of new ulcerations on the index foot
- Number of new ulcerations on the contralateral foot
- Number of new infections on the index foot
- Number of new infections on the contralateral foot
- Number and severity of falls (Hopkins Fall Grading System)¹
- Number of minor and major amputations on the index foot at the end of the follow up phase of the study
- Number of minor and major amputations on the contralateral foot at the end of the follow up phase of the study
- The number of participants in each arm requiring further intervention for CN (e.g. further immobilisation) within 6 months of remission

